9.0 Statistical Analysis Plan

9.1 Delineation of Treatment Arms

We will use block recruitment within practice sites, no more than two thirds of whom within each completed block may be medical management patients. Using block recruitment ensures that the study will be sufficiently well balanced to adequately characterize the effect of each treatment relative to the other and maintain power to evaluate primary and secondary outcomes. Each treatment arm is defined by each patient's choice of treatment at enrollment. If a patient ultimately receives a different treatment from what they chose initially, this is considered as an outcome of their initially chosen treatment. We expect that all or almost all patients who choose radical cystectomy will receive it prior to evaluation of the primary endpoint at 12 months post-enrollment, while up to 20% of patients who choose medical management may undergo radical cystectomy during this period.

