treatment effect of radical cystectomy through the creation of *potential outcomes*: two predicted outcomes for each individual patient participant, under the hypothetical assumption that they had been treated with either radical cystectomy or medical management. Next, similar to a propensity score approach, TMLE estimates the probability of treatment with radical cystectomy using either logistic regression, machine learning (LASSO, regression trees, etc.) or super learning approaches.¹⁶ In the third step of the TMLE approach, we use the probabilities obtained in the second step to update the initial estimate of each patient participant's pair of potential outcomes under each treatment group. Specifically, we will generate *targeted* estimates of the potential outcomes with regression models that incorporate both the initial potential outcome estimates and the probability of being treated with radical cystectomy. The average treatment effect is the mean difference between the updated potential outcomes and is interpreted as the causal difference in QOL if all patients had been treated with medical management versus having been treated with radical cystectomy.¹⁶ Because each patient has a pair of potential outcomes under each treatment, subgroup analyses are straightforward. As a secondary sensitivity analysis, we will evaluate these data using propensity score and G-computation methods. As a doubly robust and more efficient analytic approach relative to the comparative secondary approaches, we will use TMLE for presentation of the primary results for this study.

Longitudinal trajectories of the effect of treatment on patient QOL over time will be modeled and characterized using standard linear mixed effects models (primary analysis) or generalized estimating equations (GEE, secondary analysis). We will include covariates in the longitudinal data model to provide treatment effect estimates for subgroups of interest such as those defined by age, comorbidity, caregiver status, tumor severity, and use of investigational agents. For assessment of time-to-event outcomes (e.g., survival), we will use an extension of the TMLE approach appropriate for survival data.¹⁷

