## 4. Data Analyses

We will use descriptive statistics to characterize the treatments received, PROs, and clinical outcomes. Prior to statistical analysis, we will first compare continuous demographic and clinical characteristics by treatment group with Wilcoxon rank-sum tests to protect against violations of normality assumptions. P-values from Exact Conditional Tests, such as Fisher's exact test and its multi-degree of freedom extensions, will be used to compare categorical data.

To address treatment selection bias and potential confounding by indication in the comparison of BST vs. radical cystectomy, we will utilize targeted maximum likelihood estimation (TMLE) as the primary analytic approach for causal effect estimation using observational data. Unlike approaches that focus on creating

carefully matched treatment and control groups, TMLE allows for the inclusion of all patient participants and their reported outcome measures. TMLE first uses covariate-adjusted regression models to generate an initial estimate of the treatment effect of radical cystectomy through the creation of *potential outcomes*: two predicted outcomes for each individual patient participant, under the hypothetical assumption that they had been treated with either radical cystectomy or BST. Next, as with a propensity score approach, we will estimate the probability of treatment with radical cystectomy using SuperLearner. The SuperLearner procedure selects the best weighted combination of prediction models from among candidate learners such as logistic regression, stepwise logistic regression, generalized additive models, Bayesian GLM, LASSO, random forest, gradient descent boosting, support vector machine, and the sample mean. Finally, we will use the probabilities obtained in the second step to update the initial estimate of each patient participant's pair of potential outcomes and the TMLE estimate is interpreted as the difference in outcomes if all patients had been treated with BST versus having been treated with radical cystectomy.

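### Does the received-treatment wording of the primary TMLE conflict with analysing patients by the arm chosen at enrolment?

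*SAP*

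**What the plan says.** Both documents describe the TMLE in the language of treatment received, in three places each.

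- Potential outcomes: "under the hypothetical assumption that they had been treated with either radical cystectomy or BST" (SAP 4) and "under the hypothetical assumption that they had been treated with either radical cystectomy or medical management" (Protocol 9.2).
- Treatment model: "we will estimate the probability of treatment with radical cystectomy using SuperLearner" (SAP 4) and "TMLE estimates the probability of treatment with radical cystectomy" (Protocol 9.2).
- Interpretation: "interpreted as the difference in outcomes if all patients had been treated with BST versus having been treated with radical cystectomy" (SAP 4) and "interpreted as the causal difference in QOL if all patients had been treated with medical management versus having been treated with radical cystectomy" (Protocol 9.2).

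The exposure itself is set elsewhere. Protocol 9.1 defines each arm by the patient's choice at enrolment and says of anyone who ends up with a different treatment that "this is considered as an outcome of their initially chosen treatment". SAP 1.5 and 4.1 make the primary analysis intention-to-treat by the arm decided at enrolment, whether or not that treatment was started. SAP 4.3 adds a secondary as-treated analysis, grouped by the first treatment seen within six months, that otherwise follows the ITT approach.

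**The concern.** Choosing a treatment and receiving it are different exposures, and this study expects them to diverge: Protocol 9.1 allows that "up to 20% of patients who choose medical management may undergo radical cystectomy during this period". Nothing in the TMLE description adjusts for switching. The estimate by enrolment arm is therefore the effect of initially choosing cystectomy against initially choosing bladder-sparing therapy, while the interpretation sentence, taken literally, describes universal receipt of one or the other.

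Two features sharpen the worry. Neither SAP 4 nor Protocol 9.2 says within its own text that being treated means having chosen. And because SAP 4.3 carries the ITT approach over to the as-treated groups, one interpretation sentence appears to serve two analyses with different exposures. At stake is the stated meaning of the primary month-12 physical functioning result: a report that followed the sentence literally would claim an effect of receiving cystectomy that the primary analysis does not estimate.

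**Working it through.** **Inputs.** Planned arms of 235 (cystectomy) and 337 (medical management), total 572, with 10% missing (Protocol 9.4). Correlation 0.3, two-sided alpha 0.05, power 0.80 (Protocol 9.4). Detectable d = 0.24, equal to 5.5 points (SAP 6). Switching from medical management to cystectomy of up to 20% by month 12, with all or almost all cystectomy choosers operated on (Protocol 9.1).

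**1. The plan's own figure.** The documents do not give the formula. Assuming adjustment for baseline, so that the variance is multiplied by 1 − 0.3² = 0.91:

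- Analysed numbers: 0.9 × 235 = 211.5 and 0.9 × 337 = 303.3.
- SE = √[(1/211.5 + 1/303.3) × 0.91] = 0.0855 SD.
- Power at 0.24 = Φ(0.24/0.0855 − 1.96) = 0.802.

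The stated figure reproduces for the contrast between enrolment arms.

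**2. How far choice and receipt can diverge.**

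- Switchers at the ceiling: 0.20 × 337 = 67 (0.20 × 303.3 = 61 after the missing-data allowance).
- Cystectomy by month 12, if all 235 choosers are operated on: 235 + 67 = 302, and 302/572 = 52.8%, against 235/572 = 41.1% by enrolment arm.
- Difference in receipt between arms: 100% − 20% = 80 percentage points.

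**3. What that could mean in points (illustration only).** Suppose the effect of receiving cystectomy is d = 0.24, all cystectomy choosers receive it, and switchers carry a fraction g of the effect at month 12. The choice contrast is then 0.24 × (1 − 0.20g).

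| g | Choice contrast (SD) | Points: 5.5 × (1 − 0.20g) | Power |
|---|---|---|---|
| 0 | 0.240 | 5.50 | 0.80 |
| 0.5 | 0.216 | 4.95 | 0.71 |
| 1 | 0.192 | 4.40 | 0.61 |
| 1.5 | 0.168 | 3.85 | 0.50 |

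With full carry-over the two readings differ by 5.5 − 4.4 = 1.1 points; with no switching they coincide. The documents fix neither g nor the effect of receipt. Nor does the table show a fault in the power statement, which concerns the difference between arms as they are analysed.

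**4. Whether the text leaves the exposure open.**

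- Protocol 9.1 comes directly before the TMLE text in 9.2, defines the arm by choice and settles switching.
- SAP 1.3 defines the two arms by the patient's decision and, in the same sentence, describes their members as undergoing cystectomy or receiving BST. Protocol 9.4 likewise describes the 337 planned medical management patients as treated. This is the same shorthand as in the TMLE text.
- SAP 4 is a general method description placed above its subsections. SAP 4.1 then sets the exposure for the primary analysis, and SAP 4.3 sets it for the as-treated analysis.
- The TMLE described has one binary treatment and one treatment probability. Coding that treatment by receipt needs a time window and a rule for patients with no treatment observed. The SAP gives both only in 4.3, and only for the secondary analysis.

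The primary treatment variable can therefore be coded in only one way: the enrolment choice.

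**The case for a change.** The strongest counter-argument is that the documents do separate the two ideas when they want to. SAP 4.3 contrasts the arm a patient picks with the treatment eventually given. Protocol 9.2 itself speaks of modelling treatment choice when it turns to Hypothesis 2.1, yet of the probability of treatment in the TMLE. Hypothesis 1.1 is also framed around patients who undergo cystectomy. A reader may reasonably take different words to mean different things, and should not have to assemble the meaning of a prespecified causal estimate from several sections of two documents. The SAP also leaves the explicit switching rule to the Protocol.

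Part of this stands. Neither TMLE passage defines its own term, and the interpretation sentence is looser than the analysis it describes. The rest does not carry through to a defect. Analysing by enrolment arm under ITT already keeps switchers where they started, so the SAP's silence on later switching leaves no coding decision open. The as-treated half is weaker still: grouping by first treatment within six months already keeps a patient who starts BST and later has cystectomy in the BST group, and received-treatment wording suits that analysis better than it suits the ITT one. SAP 4.3 also states that ITT is primary and as-treated secondary, so the two estimates are labelled apart.

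**Conclusion.** No change to the plan is needed. The wording is loose, but the plan specifies one coherent primary estimate, the effect of initially choosing one option over the other with later crossover included, and a separate, lower-ranked as-treated estimate. A clause equating treatment with the enrolment choice would restate what Protocol 9.1 and SAP 1.3, 1.5 and 4.1 already establish, and would leave the data, estimator, test, sample size and power as they are.

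The distinction is real in size: up to 67 of 337 switchers, and an 80-point rather than 100-point difference in cystectomy receipt, if the 20% ceiling is reached and every cystectomy chooser is operated on. The corresponding 1.1-point gap in physical functioning also assumes a received-treatment effect of 5.5 points carried in full by switchers, which the documents do not establish. These figures are a reason for authors to phrase the primary conclusion in terms of the initial choice, as ITT reporting ordinarily does. They do not show an error in the analysis.

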## 4.1 Primary Outcome

Patient data will be analyzed according to an intention-to-treat (ITT) framework for the primary analysis, where the treatment arm is decided upon at enrollment regardless of whether that treatment was initiated. Patients that withdraw consent after enrollment and before the beginning treatment will be excluded from the ITT. Longitudinal trajectories of the effect of treatment on patient QOL over time will be modeled and characterized using standard linear mixed effects models for the primary analytic approach.

### 4.1.1 Subgroups

Because each patient has a pair of potential outcomes under each treatment, we will include covariates in the TMLE and longitudinal data models to provide treatment effect estimates for important subgroups of interest stratified by age (75 or older vs. under 75), gender (males vs. females), patients who have a caregiver (yes vs. no), and cancer severity (carcinoma in situ vs not).

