9.4 Sample Size and Statistical Power

We aim to recruit from a heterogeneous patient population that will allow for rich and broadly applicable estimation of outcomes and experiences after NMIBC that recurs after first-line BCG. **We will enroll up to 900 participants across a broad geographic recruitment area.** This cohort would represent the largest pragmatic study of recurrent high-grade NMIBC patients to date. The total sample size for CISTO is primarily motivated by statistical power considerations for **Aim 1**, comparing QOL between patients treated with medical management versus radical cystectomy. Presently, there are no guiding documents

on directly using TMLE in the calculation of statistical power for designing an observational study. The variance of the treatment effect estimate—and thus power—is a complicated function of the number treated in each group, the potential and observed outcomes, and the covariate-based probabilities of treatment with radical cystectomy. The 2:1 recruitment ratio of medical management to radical cystectomy patients at each CISTO site will ensure at least a 33% rate of radical cystectomy in the CISTO study population. However, based on actual rates of enrollment of cystectomy patients, we motivated the study sample size of 572 using 40.9% cystectomy patients in a standard two-sample repeated measures approach that will be less efficient than the analytic methods used at the time of data analysis.

Statistical power was fixed at 0.80 throughout and we considered two-sided tests with alpha=0.05 indicating statistical significance, with no adjustment for multiple comparisons for the primary question of interest. Correlation between repeated measures was assumed to be 0.3, an estimate we have observed in numerous other QOL studies. Minimal detectable effect sizes (units of QOL standard deviation) are reported in **Table 3** below for Aim 1 within subgroups with varying prevalence.

Table 3. Minimal Detectable Effect Sizes

		Subgroups		
		50%	30%	20%
Aim 1: Patient QOL	Overall	0.24	0.34	0.44

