Aim 2 is largely descriptive in nature and no statements of statistical power were considered. With recruitment of 572 patient participants, anticipating 235 radical cystectomy patients and 337 patients treated with medical management in Aim 1 and conservatively allowing for 10% missing data, this study has >0.80 statistical power to detect small differences in QOL between treatment approaches (Cohen's $d = 0.24$)²⁰ that are well below the minimally important difference of 0.5. Assuming a similar balance of treatments within subgroups, this study has >0.80 power to detect moderate but clinically important effect sizes (Cohen's $d = 0.43$) within subgroups as small as 30% of the study cohort. From SEER, large treatment effect differences would be detectable in subgroups of gender (20% female), age (52% over 75), comorbid health conditions (22% Charlson Index 1 or greater), and CIS (25%). We will plan a subgroup analysis for patients receiving investigational agents as part of a phase III clinical trial if at least 10% of participants in the medical management arm are in a trial. To inform power calculations for our secondary outcomes of bladder cancer-specific mortality, we used data from a microsimulation model demonstrating low anticipated 1-year mortality event rates (0.8% for radical cystectomy, 3.6% for continued medical management). We would have 69% power to detect a similar difference in one-year mortality due to bladder cancer and 80% power to evaluate the difference between study arms in 2-year bladder cancer-specific mortality.

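### SAP 4.1.1 rests subgroup effects on a TMLE whose only described update targets the all-patient effect, and states no subgroup-specific target or treatment-by-subgroup term

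*SAP*

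**What the plan says.** SAP section 4 describes one TMLE. "TMLE first uses covariate-adjusted regression models to generate an initial estimate"; SuperLearner is then named for the treatment probability, and one update follows. Its result is interpreted as the outcome difference had every patient received one treatment rather than the other. Protocol 9.2 likewise names the average treatment effect as the quantity estimated.

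For subgroups, Protocol 9.2 states: "Because each patient has a pair of potential outcomes under each treatment, subgroup analyses are straightforward." SAP 4.1.1 gives the same reason and continues: "we will include covariates in the TMLE and longitudinal data models to provide treatment effect estimates for important subgroups of interest". It lists age (75 or older against under 75), gender, caregiver (yes or no) and carcinoma in situ, and describes the estimates as stratified by these variables.

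Neither document states a treatment-by-subgroup term in the outcome model, a subgroup-specific update, a separate TMLE within each level, a subgroup standard error, or a contrast between levels. No interaction is stated for the mixed model either.

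**The concern.** Hypothesis 1.3 is that treatment effects differ between subgroups, and Protocol 2.1 hopes to identify which patients are best served by each treatment. The reason given for the subgroup analysis does not secure that. Two predicted outcomes per patient allow an average to be taken in any subgroup, but the average is a targeted, doubly robust estimate only if the update was made for that subgroup. Including age or gender as a covariate adjusts for it; it does not let the treatment effect vary with it. The same holds in the mixed model: without a treatment-by-visit-by-subgroup term, the model gives one common effect at each visit.

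An analyst could therefore follow the text and report subgroup effects that are near copies of the overall effect, with intervals that are too narrow. Alternatively, the analyst could report subgroup effects distorted by an error in the outcome model that the overall estimate has corrected and so does not reveal.

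**Working it through.** **1. The plan's own power figures.** Inputs from Protocol 9.4: "we considered two-sided tests with alpha=0.05 indicating statistical significance"; "Statistical power was fixed at 0.80 throughout"; "anticipating 235 radical cystectomy patients and 337 patients treated with medical management"; "conservatively allowing for 10% missing data"; "Correlation between repeated measures was assumed to be 0.3". The detectable effect is d = (1.960 + 0.842) × sqrt(1/n1 + 1/n2).

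- No missing data: 2.80 × sqrt(1/235 + 1/337) = 0.238.
- 10% missing, with variance factor 1 - 0.3² = 0.91: 0.238 × sqrt(0.91/0.9) = 0.239.
- 30% subgroup: 0.238/sqrt(0.3) = 0.435, or 0.239/sqrt(0.3) = 0.437.

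The stated 0.24 and 0.43 reproduce, to within rounding and about 1 to 2 points of power. SAP section 6 equates these to 5.5 and 9.9 points, so the SD is about 23 (5.5/0.24 = 22.9; 9.9/0.43 = 23.0). The implied standard error in a 30% subgroup is 0.43/2.80 × 23 = 3.5 points. That is the precision of a comparison made inside the subgroup.

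**2. What the update solves.** Let g be the probability of cystectomy, A the treatment (1 = cystectomy), S the subgroup, and H = A/g - (1-A)/(1-g). The update for the all-patient effect makes the sum of H(Y - Q*) zero over all patients, where Q* is the updated prediction. A subgroup effect needs that sum to be zero within the subgroup. A zero total does not imply a zero in each level: a surplus in one can offset a deficit in the other.

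If the initial regression is linear with no treatment-by-subgroup term, the predicted treatment difference is one constant, b. After a linear update it is b + e × [1/g + 1/(1-g)], where e is the fitted update coefficient. Subgroups can then differ only through their distributions of g.

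**3. Simulation.** n = 515 (572 × 0.9), 500 data sets, 30% subgroup, correct propensity model, logistic update. Nominal true effects, in points: -9.9 in the subgroup and 0 in the rest. Outcomes were truncated to 0-100, so the realised subgroup effect is somewhat smaller than nominal. These effects, the residual SD (20 points, or 15 in the last two rows) and the confounding strengths are assumptions.

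| Method | Subgroup | Rest | Difference (SD) |
|---|---|---|---|
| Pooled update, no interaction | -2.90 | -2.83 | -0.07 (0.11) |
| Same outcome model, update per subgroup | -9.40 | -0.07 | -9.33 (4.15) |
| Pooled update, interaction, correct outcome model | -9.46 | -0.03 | -9.43 (3.87) |
| Pooled update, interaction, confounder omitted from outcome model | -13.6 | +1.5 | -15.1 |
| Same outcome model, update per subgroup | -9.85 | -0.06 | -9.79 |

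At n = 20,000 the first row's difference was still -0.05, so this is bias and not noise. In the fourth row the two errors cancel overall: 0.3 × (-13.6) + 0.7 × 1.5 = -3.03, against a true 0.3 × (-9.9) = -2.97.

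**4. Other assumed effects, and coverage.** With true effects of -3 and -13 (n = 515), the pooled update without an interaction gave -6.05 and -6.06. With the interaction but a confounder omitted it gave -4.6 and -9.1, which understates the difference where the fourth row overstates it. Subgroup-targeted updates gave about -3.0 and -13 throughout.

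With the same true effects in 70% and 30% of patients and n = 572 (2,000 data sets), 95% intervals from the pooled update without an interaction covered the truth 78% of the time in the larger group and 44% to 48% in the smaller, over two runs. Subgroup-specific TMLE covered it 94% to 95% of the time. In one of those runs the SD of the estimate in the 30% subgroup was 3.52 when targeted and 1.91 when pooled; only the former matches the 3.5 in step 1. The plan states no subgroup interval method, so the coverage figures also depend on the interval used.

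**The case against.** The strongest reply is that this is silence and not a stated error. SAP 4.1.1 calls the estimates stratified, which may mean a separate TMLE within each level; a fit within a level also gives each patient a pair of potential outcomes, so the rationale does not exclude it. The power statement points the same way, because 0.43 is a within-subgroup figure. Covariate-adjusted regression does not rule out interactions, and Protocol 9.2 offers it only as an example of a prediction model. Since the covariates enter the mixed model in order to give subgroup effects, interactions may be implied there too.

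All of that stands. A reader might infer that the plan, followed as written, averages subgroup differences away. The documents do not support that: no main-effects outcome model is stated, an interaction in a correctly specified model recovers the effects, and the error can run in either direction. Nor do they support the inference that the primary result is compromised, because the overall estimate stayed correct in these simulations.

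What the reply does not answer is the rationale itself. The protocol calls subgroup analysis straightforward because the pairs exist, directly after describing a single update for the average effect. Under that update even interactions do not secure double robustness within a subgroup. If separate fits are meant, the text should say so.

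**Conclusion.** The point holds as a deficiency in the stated subgroup method and its justification. Under the pooled reading, subgroup estimates are untargeted. Without treatment-by-subgroup terms they collapse to the overall effect (a nominal 9.9-point difference came out as 0.07). With such terms and a misspecified outcome model they can be exaggerated (15.1 points) or understated (4.5 points, from -4.6 and -9.1, against a true 10).

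These sizes rest on assumed effects, SDs and confounding. The collapse without interactions follows from the form of the estimator. Whether the pooled reading is the intended one cannot be settled from the documents, so confidence is moderate. The subgroup analyses serving Hypothesis 1.3 are affected; the overall comparison on the primary endpoint is not. This should be fixed, and it is a cheap improvement.

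**What to change.** In SAP 4.1.1:

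- Define the effect in each subgroup level as its own target parameter. Estimate it by a TMLE fitted within that level, or by a joint fit with subgroup-specific clever covariates and treatment-by-subgroup terms in the outcome model.
- Report influence-curve confidence intervals for each level and for the difference between levels, since that difference is what Hypothesis 1.3 concerns.
- Add treatment-by-visit-by-subgroup terms, with their lower-order terms, to the mixed model.
- Replace the rationale, here and in Protocol 9.2, that subgroup effects follow directly from the pooled potential outcomes.

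The cost is a few lines of SAP text and code, with no new data. Intervals in small subgroups will be wider but valid. The contrast between levels will also be imprecise. With 10% missing and the 0.91 factor, its detectable size is 0.239 × sqrt(1/p + 1/(1-p)), where p is the subgroup's share of the cohort. That gives about 0.48 SD (11.0 points) at p = 50%, 0.52 (12.0 points) at 30% and 0.60 (13.8 points) at 20%, taking the SD as 23. The SAP should say this, so that a wide interval for the difference is not read as evidence of a common effect.
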